Using a parallel group RCT, we will collect data at three time points: baseline (Time 1; 0 weeks, June 2019), immediately following the BC FMNCP (Time 2; 10-15 weeks, October 2019) and 16 weeks after the BC FMNCP ends (Time 3; 26-31 weeks, February 2020).

Program overview

The BC FMNCP functions through a collaborative partnership between the BC Association of Farmers' Markets, the BC Ministry of Health, farmers' markets and community partners (i.e., local non-profit organizations). The BC Association of Farmers' Markets supports, develops and promotes farmers' markets across BC [101] and oversees the operations of the FMNCP. The FMNCP is supported by the province of BC and the Provincial Health Services Authority. Community partners distribute coupons to program participants from their organization locations (e.g., pregnancy outreach and community services agencies) on a weekly or biweekly basis and offer nutrition skill-building activities such as cooking classes or community gardens to promote nutrition- and food-related knowledge and skills.[101]

Recruitment

The FMNCP Director will identify approximately 15 BC communities for the study (from the existing FMNCP and from program waiting lists) with the aim of achieving similar rural/urban coverage as the existing FMNCP. Within each community, the FMNCP director will recruit community partners by contacting those who are members of the BC Association of Farmers' Markets and offer nutrition skill-building activities for low-income groups. Community partners within study communities will be responsible for identifying and enrolling eligible low-income adults into the study from among their existing clients and will share study details via phone, email or in-person, using posters and other recruitment aids as needed. Community partners will assess eligibility using a screening questionnaire and will obtain voluntary, informed consent from eligible participants.

Eligibility criteria

Individuals will be eligible to participate if they meet the following criteria:

- Adults (≥ 18 years)
- Low-income as determined by community-specific thresholds (~\$18,000/year annual household income before taxes)
- No expected change in household income prior to study completion
- ≤ 8 people living in the home (including the participant)
- No expected change in household composition prior to study completion
- Primary food shopper for the household
- Does not self-report dementia or Alzheimer's Disease

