- Able to speak, read and write in English (or have someone who can assist them)
- No plans to move from principal residence prior to study completion
- Has not previously participated in the BC FMNCP

Randomization

Following baseline data collection, eligible participants will be randomized to the FMNCP group (n=132) or a no-intervention control group (n=132), with a 1:1 allocation ratio. An independent researcher from the Clinical Research Unit at the University of Calgary will generate a blocked randomization sequence that stratifies participants into blocks according to sex (male, female), geographic location (rural, urban), pregnancy (yes, no) and breastfeeding (yes, no). Blocked randomization will help to ensure balanced representation of participants in study arms.[110] REDCap (Research Electronic Data Capture), a secure, web-based data collection and management application [111] hosted at the University of Calgary, will be used to randomize participants into the FMNCP and control groups on the basis of this randomization sequence. The study coordinator will subsequently communicate participant group assignments to community partners and participants. Allocation concealment will be ensured via secure storage of the randomization sequence separately from the participant database, which will only be accessible by the study coordinator and the Clinical Research Unit. Researchers will remain blinded to respondent condition throughout the study. Although participants cannot be blinded to group allocation, they will be blinded to the specific study objectives to reduce expectancy bias, whereby communication of expected study outcomes influences participants' behaviour.[112-115]

Intervention

In the existing BC FMNCP, community partners distribute one to two sheets of coupons per week (each sheet contains \$21 in coupons) to program participants for a total of 16 sheets. Coupons can be used over 16-20 weeks to purchase fruits, vegetables, dairy, meat/poultry/fish, eggs, nuts, and cut herbs at participating BC farmers' markets. However, to allow sufficient time to recruit participants for this study, community partners will distribute 16 coupon sheets to the FMNCP group over 10-15 weeks (households with 5-8 individuals will receive 32 coupon sheets). To ensure participants receive all 16 coupon sheets,

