Participants will complete two unannounced dietary recalls at each time point. Twenty-four hour dietary recalls are a recommended dietary assessment method to evaluate the effect of an intervention on diet quality, as they have less systematic error than other self-reported dietary assessment tools.[150, 151] Administration of unannounced dietary recalls minimizes reactivity bias, where participants adjust their dietary intake in anticipation of having to report it.[152]

Participants will record all foods and beverages consumed (excluding supplements) from midnight to midnight the previous day using Health Canada's validated Automated Self-Administered 24-hour Dietary Recall (ASA24-Canada-2018),[151, 153-155] an automated online dietary assessment tool.[154, 155] The ASA24 collects information regarding dietary intake in a series of four steps: 1) foods consumed at each meal/snack, 2) queries regarding omitted meals/snacks, 3) details (e.g., cooking methods, portions), and 4) review of commonly forgotten items.[151, 156] The ASA24 concludes with a question querying

whether reported intake was less than usual, usual, or more than usual.[156] The ASA24 has been used with older, multi-ethnic, and disadvantaged adults [113-115, 151, 157] and was preferred by a majority of participants compared to interviewer-administered recalls;[113] however, in a recent study among BC FMNCP participants, we identified several usability issues with the ASA24.[116] For example, participants reported difficulties in searching for specific foods and making changes to entered meals.[116] We will aim to address these challenges by including a pictorial user guide in survey invitation emails, and by training community partners to assist participants in-person with the ASA24-Canada-2018. Further, participants and community partners will have access to a toll-free study helpline available 10 hours/day, 6 days/week during data collection. Helpline operators will provide assistance via telephone or email, and include three registered dietitians and the study coordinator, all of whom completed a half-day training session. Interrater reliability in entering meals into the ASA24-Canada-2018 among the helpline operators was high, with an intraclass correlation of 0.98.

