The purpose of the helpline is two-fold: 1) to serve as a support platform for community partners to ask questions and update researchers, and 2) to assist participants in completing data collection. If needed, helpline operators will verbally read all questions to participants and enter their responses online on their behalf. To maintain blinding, operators will remind participants not to disclose their group assignment during the call. Supporting participants during data collection will help to minimize missing and inaccurate data and participant attrition. To further minimize attrition, if data collection is not completed within 48-hours of the initial prompt, researchers will make up to four attempts to contact participants by email and/or phone. Community partners will also remind participants to complete data collection.

Data collected by community partners and farmers' market vendors

Community partners will maintain records of the number of coupons distributed to each participant (by recording the unique bar code number on each coupon) and the frequency and types of nutrition skill-building activities attended. Farmers' market vendors will track coupon redemption and foods purchased with coupons (e.g., fruits, vegetables, dairy) by using checkboxes on the back of each coupon. Farmers' market managers will collect redeemed coupons from vendors and submit them to the FMNCP. They will complete tracking sheets noting the number of coupons redeemed and foods purchased with coupons.

Statistical analysis plan

Healthy Eating Index-2015

Diet quality scores and subscores will be calculated using the validated Healthy Eating Index-2015 (HEI-2015),[158-162] a tool used to assess conformance with the 2015-2020 Dietary Guidelines for Americans.[161] HEI-2015 subscores will be examined to gain insight into the specific dietary components that change in response to the intervention.[163] HEI scores are associated with indicators of socioeconomic position [164] and chronic disease.[18, 160, 165-168] Although Canadian adaptations of the HEI have been developed, they have either not been validated, are not density-based, or reflect dietary recommendations that are no longer current.[9, 169] Given that dietary recommendations in Canada and the U.S. are similar,[170-172] the HEI-2015 remains an appropriate tool to assess diet quality of Canadians.[9]

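### At Times 2 and 3, in-person recall help and reminders from community partners who know the allocation are permitted, unblinded and unlogged, and could differ between arms

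*Combined protocol and SAP*

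**What the plan says.** All references are to the combined protocol and SAP.

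- **Randomization:** "Following baseline data collection, eligible participants will be randomized". Then: "The study coordinator will subsequently communicate participant group assignments to community partners and participants". Researchers are to stay blinded; community partners are not mentioned in that statement.
- **Program overview and Intervention:** partners hand out coupons "on a weekly or biweekly basis and offer nutrition skill-building activities such as cooking classes or community gardens". Controls receive neither coupons nor activities but keep their usual meetings with the partner.
- **Data collection:** a partner site is encouraged at baseline. At Times 2 and 3 the prompt is an email and participants choose where to respond. The sentence on partners recording the place of completion sits in the description of baseline.
- **Dietary intake:** the response to known ASA24 usability problems includes a pictorial guide, a helpline, and help in person, "by training community partners to assist participants in-person with the ASA24-Canada-2018". No time point is attached. Helpline operators are to ask callers not to reveal their group. On retention, after up to four researcher contacts: "Community partners will also remind participants to complete data collection".
- **Statistical analyses:** models adjust for data collection mode (online or phone) and place (community partner or other).

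**The concern.** HEI-2015 is the primary outcome and is scored entirely from what is entered in the recall. Someone helping a participant find foods or edit meals can influence what is entered. Several adequacy components (fruit, vegetables, dairy, protein foods) overlap with what coupons can buy. Participants cannot be blinded, so a helper who also knows the arm adds a second route to bias, and this one is avoidable.

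Reminders raise a related issue. The FMNCP arm has programme visits at which a reminder or an offer of help can easily be given. If that happened, completion could differ by arm for reasons tied to programme contact, and an in-person prompt could weaken the unannounced nature of the recalls.

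**Working it through.** **Step 1. Who knows the allocation, and who may help with the recall?**

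| Role | Knows the arm? | Contact with the recall | Stated safeguard |
|---|---|---|---|
| Researchers | No, by statement | Email and phone follow-up | Blinded throughout |
| Helpline operators (three dietitians) | Not stated that they do | Read questions, enter answers | Ask callers not to disclose group |
| Study coordinator | Yes, communicates assignments | Also a helpline operator | Same request, which cannot blind someone who already knows |
| Community partners | Yes, told assignments | In-person help, reminders | None stated |

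**Step 2. When does it matter?**

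- Time 1: recalls precede randomization, so help is neither unblinded nor arm-dependent.
- Time 2: follows 10-15 weeks in which the FMNCP arm collects coupons "on a weekly or biweekly basis" and is invited to activities. More partner contact in that arm is a fair inference.
- Time 3: 16 weeks after the programme ends. Coupon visits have stopped, so the contact gap should shrink. Help given then is still unblinded.

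**Step 3. Do the planned covariates deal with it?** Only in part.

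- Place does not show whether help was given.
- The recording of place is described only for baseline.
- At follow-up, place is a post-randomization variable.
- Mode has two levels, online and phone. In-person help on the web platform would presumably be coded online.

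**Step 4. What would a given shift do?** This step is illustration only. The documents give neither the share of recalls assisted nor the effect of assistance on the score.

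Inputs from Sample size calculation: N = 264 (132 per arm), power 80%, type I error 5% (two-sided assumed), difference 4.7, attrition 30%, design effect 1.1. No SD is given, so N cannot be reproduced independently and the SD is back-solved.

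- Effective n per arm = 132 × 0.70 / 1.1 = 84.0
- Implied SE = 4.7 / (1.960 + 0.842) = 1.68 points
- Implied SD = 1.68 / √(2/84) ≈ 10.87. As a check, SD 10.8 gives N = 262 and SD 10.9 gives N = 268. If attrition is applied as a multiplier of 1.3, the SD is about 11.4 and the SE is unchanged.

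With no true effect and a spurious between-arm shift b, the rejection rate is Φ(−1.96 + b/SE) + Φ(−1.96 − b/SE):

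| Assumed shift b (HEI points) | Share of 4.7 | Two-sided rejection rate |
|---|---|---|
| 0.5 | 11% | 6.0% |
| 1.0 | 21% | 9.2% |
| 1.5 | 32% | 14.5% |
| 2.0 | 43% | 22.2% |

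One way to obtain a shift is (difference in assisted share) × (effect of assistance on the score). A 20-percentage-point gap with an effect of 1 to 3 points gives 0.2 to 0.6 points, which is 4% to 13% of 4.7. If assistance moved the score only in the FMNCP arm, assisted shares of 20% to 60% with the same 1 to 3 points would give 0.2 to 1.8 points, or 4% to 38%. That model sets the control-arm shift to zero, and nothing in the documents supports doing so.

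**The case against.** A reader might infer that assistance is in fact unequal between arms and inflates the FMNCP result. The documents do not support that.

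- **Inequality is not stated.** Training and reminders apply to participants generally, and controls keep meeting their partner. More contact in the coupon arm is one inference; more recall help is a second inference on top of it.
- **Targeted prompting is not shown.** A reader might suppose that partners know what the coupons bought. Vendors mark the foods purchased and market managers collect the coupons. Partners record only coupons distributed and activities attended. Any stake they have in the programme's success is inferred from their role.
- **Direction is open.** HEI components are scored per unit of energy and four of them are moderation components, so fuller entry can lower the score as well as raise it. ASA24 itself asks about omitted meals and commonly forgotten items, and the reported usability problems were searching and editing, not remembering.
- **Central contact already exists:** email prompts, up to four researcher attempts, and gifts before Times 2 and 3. Attrition has multiple imputation, inverse probability weighting and pattern-mixture analyses planned.
- **Assistance may be harmless.** The reference list includes a study whose title says that help does not substantially affect ASA24 accuracy in women with low incomes. Going by its title, it does not address helpers who know the arm.

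These points remove any claim about size or direction. They do not supply a safeguard for partners or a record of their help. The missing-data analyses address absent recalls, not recalls shaped by a helper.

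**Conclusion.** The concern holds as a gap in blinding and record-keeping at Times 2 and 3. Partners know the allocation, deliver the programme to one arm, may help with the primary-outcome recall, and fall outside every stated blinding safeguard. Without a log, neither the investigators nor a reader could tell afterwards whether help differed by arm. The risk is most plausible at Time 2 and weaker at Time 3; baseline is sound.

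No figure in the plan is put in error. The shifts and rejection rates above rest on assumed inputs and on an SE implied by the stated power, so they show sensitivity and do not estimate bias. In particular, 38% of the target effect should not be quoted as the likely size. The change is worth making because it is cheap and protects the primary outcome.

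A related and firmer point is that the study coordinator both communicates assignments and staffs the helpline, so the helpline as described is not fully blinded either.

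**What to change.** Amend Dietary intake and the retention text that follows the helpline description:

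1. Keep partner help with ASA24 at Time 1.
2. At Times 2 and 3, limit partners to a device, internet access, a private space and log-in support. Route help with recall content to the existing helpline, taken by operators who do not know the allocation. The study coordinator should not take these calls.
3. Make the partner reminder a scripted contact on the same schedule in both arms that does not announce the recall day, or rely on the existing central email and phone contacts.
4. Record for every recall whether help was given and by whom, and report this by arm and time point. State that place is recorded at all three time points.
5. Add a sensitivity analysis by assistance, labelled as conditioning on a post-randomization variable. Simply excluding assisted recalls could itself introduce bias if help depends on arm.

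**Cost:** protocol and training wording, one or two fields per recall and one extra analysis. The helpline will take more calls. Some in-person support is lost, which could slightly affect completion in a trial that already assumes 30% attrition and admits people who need help with English. Where in-person help is unavoidable, allow it with a neutral script and log it.

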The HEI-2015 encompasses thirteen dietary components to assess overall diet quality,[161] including nine 'adequacy' components (recommended foods/nutrients, including total fruits, whole fruits, total vegetables, greens and beans, whole grains, dairy, total protein foods, seafood and plant proteins, fatty acids) and four 'moderation' components (foods/nutrients recommended to limit, including refined grains, sodium, added sugars, saturated fats). Component scores are density-based and, therefore,

independent of energy intake.[161, 163] Diet quality (total HEI-2015 scores and subscores) will be calculated using the simple HEI scoring algorithm.[161] This method provides scores at the individual level and can, therefore, accommodate the multi-level nature of our data and include covariates.[161] HEI-2015 scores will be calculated using three nutrient databases linked to the ASA24-Canada-2018:[173] the Canadian Nutrient File and the U.S. Department of Agriculture's (USDA) Food and Nutrient Database for Dietary Surveys to convert dietary intakes to energy and nutrient intakes, and the USDA Food Patterns Equivalents Database to convert dietary intakes to dietary constituents (e.g., fruits) and measurement units consistent with HEI-2015 scoring standards (e.g., cup-equivalents of fruit).[162, 163, 174, 175] Ratios for each of the dietary constituents (e.g., quantity of fruit per 1000 kcal) will be calculated for each participant and scored using HEI-2015 scoring standards. The total score for each participant will be derived by adding the scores for intake of 'adequacy' and 'moderation' components with possible scores ranging from 0-100. A higher score indicates a higher quality diet.[161]

Statistical analyses

Descriptive analyses will be conducted to examine participant characteristics by group at each time point. Characteristics of study completers (i.e., provided data at Time 3) and non-completers will also be compared.

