Analyses will be intention-to-treat, in which participants will be analysed within the groups to which they were randomized regardless of adherence (e.g., failure to redeem coupons) or dropout. The analyses will include all participants who provided data at baseline. Repeated measures mixed-effect regression will assess differences in changes in mean HEI-2015 scores, HEI-2015 subscores, mental well-being, sense of community, and subjective social status between the FMNCP and control groups immediately post-intervention and 16 weeks post-intervention. Multinomial logistic regression will be used to assess

differences in the odds of experiencing household food insecurity and malnutrition risk for the FMNCP group compared to the control group immediately post-intervention and 16 weeks post-intervention. Statistical models will include intervention group (FMNCP vs control), time from baseline, intervention-by-time interaction, blocking variables (i.e., sex, rural/urban, pregnancy, breastfeeding), baseline values of the outcome, data collection mode (online, phone), household size, and place of data collection (community partner, other) as fixed effects covariates. Participant-specific (i.e., repeated measures) and rural/urban variations in outcomes will be modeled using random effects. Models will also include covariates specific to each outcome to increase the precision of estimates.[95] For the primary outcome of overall diet quality, models will include children living in the home (yes, no), sex, age, BMI, marital status, race/ethnicity, perceived health, smoking, day of dietary recall completion, and dietary recall number (i.e., dietary recall 1 or 2). Models that are and are not adjusted for an indicator of energy intake misreporting (the ratio of reported energy intake to total estimated energy expenditure) will be presented. Adjusted group differences (i.e., FMNCP vs control) in outcomes will be estimated using 95% confidence intervals and corresponding p-values.

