Subgroup analyses will examine whether the impact of the intervention on primary and secondary outcomes differs according to age group or sex. Dose-response analyses will examine whether the impact of the BC FMNCP on overall diet quality depends on the number of coupons redeemed and the number of nutrition skill-building activities attended. Interactions will be retained in statistical models if $p < 0.10$. Analyses will be conducted in Stata (v15.1, Stata Corp, TX, USA), with $p < 0.05$ indicating statistically significant differences between groups.

Missing data

Missing data will be handled using full information maximum likelihood under a missing at random assumption. We will also attempt to minimize missing data by reviewing all data within 24 hours of receipt and by contacting participants to fill-in missing or implausible responses within 48 hours. Participants who drop out of the study will be asked to provide reasons for drop out to assess the plausibility of a missing at random assumption.

Sensitivity analyses

Monte Carlo Markov Chain multiple imputation, inverse probability weighting and available case analysis will be used in a sensitivity analysis to investigate the impact of different assumptions about missing data on estimated program impacts.[176-178] Given the possibility of non-random attrition, pattern mixture methods models [179] will be used to explore the robustness of study findings to the assumption that data were missing not at random.[180]

Sample size calculation

The sample size was calculated from a RCT that investigated the impact of a fruit and vegetable rebate on HEI-2010 scores in low-income participants in the U.S.,[95] and a cross-sectional study that assessed average diet quality scores in disadvantaged Canadians.[36] In the RCT, diet quality in the intervention group was 4.7 points higher (95% CI 2.4, 7.1) at follow-up compared to controls.[95] This difference can be translated to, for example, an additional half serving of fruit per day, which is clinically meaningful and achievable.[107, 165] Assuming a type I error of 5%, an attrition rate of 30% by the 26- to 31-week follow up, and potential design effects based on sampling within different communities (estimated at 1.1, or an inflation of 10%), 264 participants are required for 80% power to detect a 4.7-point difference in diet quality.

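### The primary HEI-2015 model implies two recall rows per visit but names no term for recalls from the same visit, so the follow-up intervals may be slightly too narrow

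*Combined protocol and SAP*

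**What the plan says.** Under Data collection and Dietary intake, each participant completes two 24-hour recalls at each of three time points, the second 2-5 days after the first. Under Study design, the time points are June 2019, October 2019 and February 2020.

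Under Statistical analyses, continuous outcomes are analysed by repeated measures mixed-effect regression, with the baseline value of the outcome among the fixed covariates. The primary outcome has further covariates ("For the primary outcome of overall diet quality, models will include children living in the home" and others), ending with "day of dietary recall completion, and dietary recall number (i.e., dietary recall 1 or 2". The random part is given in one sentence: "Participant-specific (i.e., repeated measures) and rural/urban variations in outcomes will be modeled using random effects". Nothing says whether the participant term is an intercept or an intercept plus slope. No visit-level term, residual covariance or robust variance is named. Results are reported so: "Adjusted group differences (i.e., FMNCP vs control) in outcomes will be estimated using 95% confidence intervals and corresponding p-values".

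Two other statements bear on the point. Under Healthy Eating Index-2015, the dietary ratios "will be calculated for each participant and scored using HEI-2015 scoring standards", which does not say whether the two recalls are scored separately or combined. In the fixed-effects list, rural/urban appears among the "blocking variables (i.e., sex, rural/urban, pregnancy, breastfeeding", one sentence before it appears as a random effect. Under Randomization it has two levels.

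**The concern.** Recall number can take a value only if each recall has its own row. With two rows per visit there are two layers of correlation: between rows from the same person, and additional correlation between rows from the same person at the same visit. Season, income timing or household circumstances could make two recalls in one week more alike than recalls from October and February. Recall number as a fixed covariate shifts the mean and does nothing for this correlation.

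A participant intercept alone forces one common correlation on all pairs of rows within a person. The second recall of a visit is then credited with more independent information than it has, and the interval for the group difference at that visit is too short. If the share of variation between visits is above zero, the error goes only in that direction. A second consequence is that two analysts following the same sentence could report different intervals for the primary outcome.

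**Working it through.** The plan gives no figure to reproduce on this point: no HEI-2015 standard deviation, variance share or within-person correlation. The shares below are assumptions.

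**Set-up.** Outcome rows are Time 2 and Time 3 with two recalls each, and the baseline mean of two recalls is a covariate. Let *p*, *v* and *e* be the participant, participant-by-visit and recall-residual variances, with total 1. Assume *e* = 0.60 and *p* + *v* = 0.40, with *v* = 0, 0.05, 0.10 or 0.20.

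**What an intercept-only model does with *v*.**
- Each person has four rows and 3 within-person degrees of freedom. One is between visits (mean square *e* + 2*v*) and two are within visits (mean square *e*).
- The fitted residual is [(*e* + 2*v*) + 2*e*]/3 = *e* + 2*v*/3, and the fitted participant variance is *p* + *v*/3.
- The model variance of a visit mean is therefore *p* + *v*/3 + (*e* + 2*v*/3)/2 = *p* + 2*v*/3 + *e*/2. The true variance is *p* + *v* + *e*/2.
- Adjusting for the baseline mean replaces *p* by *p*′ = *p* − *p*²/(*p* + *v* + *e*/2).

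The SE ratio is √[(*p*′ + 2*v*/3 + *e*/2)/(*p*′ + *v* + *e*/2)], and two-sided alpha is 2[1 − Φ(1.96 × SE ratio)].

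| *v* | *p*′ | model variance | true variance | SE ratio | SE too small by | alpha |
|---|---|---|---|---|---|---|
| 0 | 0.171 | 0.471 | 0.471 | 1.000 | 0% | 5.0% |
| 0.05 | 0.175 | 0.508 | 0.525 | 0.984 | 1.6% | 5.4% |
| 0.10 | 0.171 | 0.538 | 0.571 | 0.970 | 3.0% | 5.7% |
| 0.20 | 0.143 | 0.576 | 0.643 | 0.947 | 5.3% | 6.4% |

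Setting *p* + *v* to 0.30 or 0.50 gives alpha of 5.4%, 5.7-5.8% and 6.4%.

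**Simulation check.** Settings: 264 participants allocated 1:1, no effect, 30% of visits missing at Time 3 (the plan's attrition rate) and 15% at Time 2 (assumed), maximum likelihood, 10,000 trials per setting, Monte Carlo error about 0.23 points. Cells show alpha at Time 2 / Time 3.

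| *v* | intercept only | plus participant-by-visit intercept |
|---|---|---|
| 0 | 5.4 / 5.8% | 5.3 / 5.7% |
| 0.05 | 5.7 / 5.6% | 5.3 / 5.1% |
| 0.10 | 5.5 / 6.2% | 4.9 / 5.3% |
| 0.20 | 6.3 / 6.6% | 5.2 / 5.3% |

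On the same datasets, omitting the visit term adds 0.1, 0.3-0.5, 0.6-0.9 and 1.1-1.4 points. At a 5% share the simulated alpha cannot be told apart from that at zero share. A participant intercept plus time slope with free covariance gives 4.9-5.5% at the 5-20% shares, with intervals 1.5-1.7%, 2.8-3.2% and 5.1-5.7% wider than intercept only.

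**In HEI points.** Sample size calculation gives 80% power for 4.7 points. This implies an SE of about 4.7/(1.96 + 0.84) = 1.68 and a half-width of about 3.3. Widening by 1.5% to 5.9%, the simulated range for adding the visit term, is about 0.05 to 0.19 points.

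**If baseline is also an outcome row.** There are then six rows and 5 within-person degrees of freedom. The fitted residual is [2(*e* + 2*v*) + 3*e*]/5 = *e* + 0.8*v*. For a change between two visits the variance ratio is (*e* + 0.8*v*)/(*e* + 2*v*), giving alpha of 6.1%, 7.1% and 8.8%.

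**Rural/urban.** One simulated dataset (264 participants, residual variance 1) had the factor both fixed and random. The maximum-likelihood log-likelihood falls from −366.68 at random variance 0 to −369.31 at 0.1, −371.54 at 1 and −376.14 at 100, so the estimate goes to zero. The REML log-likelihood is flat at −370.86, so there the variance is not identified. The treatment SE is 0.1245 throughout.

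**The case against.** The strongest reply is that the error needs three conditions together: recall-level rows, an intercept-only participant term, and a non-zero visit share. The plan states none of them outright. The Healthy Eating Index-2015 section can be read as one score per participant per visit, which removes the problem. A random slope would absorb it. The plan also describes its data as multi-level, so the authors were aware of clustering. Even when all three hold, the effect is at most about 0.2 HEI points on the half-width.

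Most of this stands and keeps the point minor. It does not remove it. Recall number has no value to take under a combined score, so the plan's own covariate list favours recall-level rows. An intercept is a natural reading of a participant-specific random effect, and the choice should not be left until the data are seen.

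Three stronger readings are tempting and not supported:

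- **Type I error of 7% or more.** At these shares that follows if baseline is an outcome row, or for a Time 3 versus Time 2 contrast. The plan speaks of differences in changes, but lists the baseline value as a covariate, and the objectives ask for group differences at each follow-up.
- **Rural/urban distorts the treatment comparison.** Neither the treatment estimate nor its SE moves. Under Missing data the plan names maximum likelihood ("Missing data will be handled using full information maximum likelihood under a missing at random assumption"), under which the extra variance goes to zero.
- **Questionnaire outcomes share the defect.** They have one value per visit, so there are no same-visit pairs. This includes the outcomes analysed for "differences in the odds of experiencing household food insecurity and malnutrition risk for the FMNCP group compared to the control group".

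**Conclusion.** The concern holds as a minor one. As written, the primary model implies two rows per visit and names no term for their shared correlation. Read as a participant intercept, it gives intervals at each follow-up that are slightly too narrow whenever diet varies between visits. The size rests wholly on assumed shares: an SE about 1.6% to 5.3% too small for visit shares of 5% to 20%, with closed-form alpha of about 5.4% to 6.4%. It is nil at zero share or with one combined score per visit, and largely absent with a random slope. The rural/urban double listing is a redundancy to tidy. A reader might infer that the trial's primary conclusion is at risk, but nothing in the documents or in these figures supports that.

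**What to change.** For HEI-2015 models (total score and subscores) fitted with one row per recall, state that the model has a participant random intercept and a participant-by-visit random intercept nested within it (in Stata, `|| id: || visit:`). Define the baseline covariate as the mean of the two baseline recalls, since the plan does not say how two recalls become one baseline value.

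If one combined HEI-2015 score per visit is intended, say so and drop recall number. The participant effect is then enough, and recall day could stay only as a visit-level summary.

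Keep rural/urban as a fixed effect only. If the random term was meant for community (about 15 are planned under Recruitment, and the sample size carries a design effect of 1.1 for sampling within communities), write community. No change is needed for questionnaire outcomes.

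The cost is a small change to the SAP text, no new data and one more variance parameter, which may be estimated at zero. In simulation the intervals widen by 0.5-0.6% if the visit share is zero, and by 1.5-1.8%, 2.8-3.3% and 5.1-5.9% at shares of 5%, 10% and 20%.
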